4 STUDY DESIGN

4.1 OVERALL DESIGN

The primary study hypothesis is that the time to achieve RTS criteria for pediatric patients with apophysitis of the knee who receive iontophoresis with DSP treatment and PT will be different than those who receive placebo or PT alone. The secondary study hypotheses are: that the patient reported outcomes for pediatric patients with apophysitis of the knee who receive iontophoresis with DSP treatment and PT will be different than those who receive placebo or PT alone; and the frequency and intensity of adverse events among pediatric patients with apophysitis of the knee who receive placebo or PT alone.

This is a Phase II trial. It is a three-arm, randomized, double-blind, placebo-controlled comparison study looking at the functional and patient reported outcomes of iontophoresis (with DSP or placebo) in conjunction with PT versus PT alone to treat pediatric patients diagnosed with apophysitis of the knee.

The study is double-blinded and placebo-controlled to minimize bias. There will be three (3) study groups

- Iontophoresis using DSP (study drug) + PT
- Iontophoresis using placebo + PT
- o PT alone

Participants in all three groups will receive the standard PT protocol for apophysitis of the knee. This will involve up to 20 visits. Participants randomized to the iontophoresis groups will receive up to 12 iontophoresis treatments over a maximum of eight (8) weeks. All participants will receive a phone follow-up call 30 days after they meet RTS criteria as well as an electronic survey follow-up 90 days after they meet RTS criteria.

This study will only be conducted through the Children's Hospital of the King's Daughters Sports Medicine PT Department with study-related activities occurring at six of CHKD's Hampton Roads PT clinics. All study-related activities will be completed by Physical Therapists and Physical Therapist Assistants (Treating Therapists) trained on the protocol and CITI trained.

Concomitant therapies, age, gender, and race will be conducted to analyze the possible effects of these covariates on length of time to RTS

Stratifications of age, gender, and race will be conducted to analyze the possible effect of these covariates on length of time to RTS as well as on patient reported outcomes LEFS, Godin Leisure-Time Activity, and FACES Pain Scale and on safety outcomes.

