6.3 MEASURES TO MINIMIZE BIAS: RANDOMIZATION AND BLINDING

A center-stratified randomization method will be used to maintain balance between treatment groups and centers. Equal number of participants per intervention will be considered to maximize study power. The CHKD Pharmacy Department will hold the randomization key and will prepare bottles of study drug and placebo (see Section 6.2.2 Formulation, Appearance, Packaging, and Labeling).

Treating therapists will assign randomization codes in chronological order as participants enroll in the study. Since the study drug and sodium chloride are identical in appearance, the Treating Therapists will

be blinded to study assignment. Those participants assigned to "Group C", or standard PT alone, will be unblinded to treatment as they will not receive iontophoresis.

In the case of an unexpected and serious adverse event in which knowing the study assignment is critical to the medical care of the participant, the CHKD pharmacist may release this information to the Independent Safety Monitor only, who may share this information with the treating physician.

Both the Treating Therapist and the participants assigned to one of the two iontophoresis groups will be blinded to study treatment. The DSP injection and 0.9% sodium chloride injection are clear, colorless liquids that will be supplied by the CHKD Pharmacy Department in identical looking single-use bottles. Each bottle will contain 1.8 mL of solution and will be labeled in a blinded fashion as either lontophoresis Study Drug "A" or "B".

In this study, the Treating Therapists will also perform all physical therapy assessments. While having a separate group of "assessing therapists" and "treating therapists" minimizes bias even further than the current study design, combining their roles is preferred as it reduces error by minimizing the number of therapists involved, improves completion consistency of the RTS Criteria Checklist, and minimizes scheduling conflicts caused when trying to coordinate two therapist's schedules for every study visit conducted.

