9.3 POPULATIONS FOR ANALYSES

A Modified Intention-to-Treat Analysis Dataset will be utilized, so that participants who received at least one dose of study intervention will be included in the analysis dataset.

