9.4.2 ANALYSIS OF THE PRIMARY EFFICACY ENDPOINT(S)

A GLM will be conducted to test for significant difference in time to RTS (in days) between pediatric patients with apophysitis of the knee who receive iontophoresis with DSP treatment and PT and those

who receive placebo or PT alone. The result will be presented as average time to RTS with 95% confidence interval for intervention groups. Non-informative censoring will be checked to ensure mechanism of censoring is independent of treatment groups.

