9.4.5 BASELINE DESCRIPTIVE STATISTICS

Age at admission and baseline patient reported outcomes will be compared between treatment groups using Analysis of Variance (ANOVA) test. Chi-square test will be conducted to test comparability of intervention groups in terms of gender and race distribution. Continuous variables will be presented as mean and standard deviation. Categorical variables will be expressed as frequency and percentage. All tests will be two-sided and p < 0.05 will be considered statistically significant.

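### Randomisation is stratified by clinic, but the primary time-to-RTS model names neither clinic nor any baseline covariate: a modest, avoidable loss of precision

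*Combined protocol and SAP*

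**What the plan says.** Section 6.3 states that "A center-stratified randomization method will be used to maintain balance between treatment groups and centers" and, on the allocation ratio, that "Equal number of participants per intervention will be considered to maximize study power". Section 4.1 has "study-related activities occurring at six of CHKD's Hampton Roads PT clinics", so there are six strata.

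Section 9.4.2 gives the primary analysis: "A GLM will be conducted to test for significant difference in time to RTS (in days) between pediatric patients with apophysitis of the knee". It adds that "The result will be presented as average time to RTS with 95% confidence interval for intervention groups". It lists no model terms beyond treatment group, and it expects some censoring: "Non-informative censoring will be checked to ensure mechanism of censoring is independent of treatment groups".

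Baseline data are available. Section 9.4.5 says "Age at admission and baseline patient reported outcomes will be compared between treatment groups using Analysis of Variance (ANOVA) test". Age enters a time-to-RTS model only in section 9.4.6, under sub-group analyses, together with gender, race and concomitant therapies. Clinic appears in no model in section 9.4.

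**The concern.** Stratifying by clinic balances the arms within each clinic, so the treatment contrasts vary less from trial to trial than under simple randomisation. A model without clinic does not see this. It counts between-clinic differences as residual noise and reports a standard error that is too large. The plan pays for the stratification and then discards its benefit, although section 6.3 itself cites power as a design aim.

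The stake is precision only. The omission does not bias the treatment comparison or raise the false-positive rate. Because 9.4.2 is silent on covariates, it also leaves the choice of model open until the data are in.

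**Working it through.** **Inputs.** From section 9.2: N = 126, f = 0.28, 80% power, alpha 0.05, total 147 after inflation. Three arms; six clinics (4.1). The share of outcome variance explained by clinic, R², is not in the protocol. I assume 0, 2, 5, 10 and 20%.

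**1. The plan's own figure.** Three-group F test with df = 2 and N − 3, noncentrality λ = N f². At N = 126, λ = 126 × 0.0784 = 9.878, df = 2 and 123, critical F = 3.070, power = 80.02%. At N = 125 power is 79.68%. The 126 is therefore reproduced, and it is the sample size of an unadjusted model.

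**2. With clinic fitted.** Five more degrees of freedom go to clinic (df = 2 and N − 8), and the residual variance falls to 1 − R², so λ = N f² / (1 − R²). At R² = 5%, λ = 9.878 / 0.95 = 10.398, df = 2 and 118, critical F = 3.073, power = 82.09%. The interval ratio is √(1 − R²) × t(118)/t(123).

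| Clinic share R² | Power, N = 126 | N for 80% power | Interval width, with / without clinic | Power, N = 147 |
|---|---|---|---|---|
| 0% | 79.98% | 127 | 1.000 | 86.17% |
| 2% | 80.82% | 124 | 0.990 | 86.89% |
| 5% | 82.09% | 120 | 0.975 | 87.96% |
| 10% | 84.22% | 114 | 0.949 | 89.70% |
| 20% | 88.42% | 102 | 0.895 | 92.97% |

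Without clinic, the formula gives 80.02% at N = 126 and 86.20% at N = 147. The larger N matters because section 9.3 says "participants who received at least one dose of study intervention will be included in the analysis dataset", so more than 126 may be analysed.

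**3. Simulation of the omission.** Normal, fully observed outcome, N = 126, random clinic effects, total variance 1, arms balanced within clinics, 60,000 replicates. Clinics are equal (7 per arm) or unequal (14, 10, 8, 5, 3, 2 per arm).

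| Share | Type I error without clinic (equal; unequal) | Power without v with clinic (equal) | Power without v with clinic (unequal) |
|---|---|---|---|
| 2% | 4.77%; 4.80% | 80.3 v 80.9% | 80.3 v 80.8% |
| 5% | 4.42%; 4.47% | 80.6 v 82.1% | 80.7 v 82.0% |
| 10% | 3.86%; 3.96% | 81.2 v 84.3% | 81.4 v 84.2% |
| 20% | 2.85%; 3.02% | 82.5 v 88.4% | 82.8 v 88.4% |

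A separate simulation used permuted blocks of three within unequal clinics (8,000 null and 6,000 alternative replicates). Type I error without clinic was 4.6, 4.4, 3.5 and 2.7% at these shares, against 4.8 to 5.2% with clinic. Mean error in the treatment contrast was at most 0.01 SD, within simulation error.

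**4. With censoring at week 8.** Assume 10% or 30% do not meet RTS. Log-normal regression with clinic as a fixed effect (N = 126, 1,500 replicates per cell) gains 0.3–0.7, 1.3–1.7, 2.5–3.6 and 5.6–6.6 points at shares of 2, 5, 10 and 20%. It changes by 0 to −0.2 points if clinic explains nothing. A log-rank test stratified by clinic behaves differently. It loses 0.9–1.6 points at a share of 0 and 0.1–0.9 at 2%, then gains 0.2–0.8 at 5%, 2.3–2.8 at 10% and 5.7–6.3 at 20%.

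**5. Age.** One degree of freedom at N = 126. If age explained 2% or 5% of variance (assumed; the protocol supports no value), power would be 80.86% or 82.13%. If clinic and age together explained nothing (6 df), power would be 79.97%, and N = 127 would restore 80%.

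**The case against.** The strongest case against is that nothing planned fails. The 126 is right for an unadjusted model, alpha is kept, and if all 147 are analysed the simulated power without clinic is already 86.5% or more. The protocol itself points to a small clinic share: one department, a standardised therapy progression (8.1), full review of RTS checklists (10.1.6) and shared training (10.1.7). On that reading only the 2–5% rows are realistic. This stands, and it is why the point is modest. It does not rule out a larger share. Treating therapists assess their own patients (6.3), and the checklist in 12.3 includes judgement items such as landing quality and trunk position, so assessor differences could follow clinic.

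Second, 9.4.2 is silent rather than expressly unadjusted, and 9.4.6 has a covariate model for the same endpoint. That is true. But the 9.4.6 model is labelled sub-group, includes concomitant therapies that section 6.5 records at each visit after randomisation, and also omits clinic.

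Third, the case for age is weaker than the case for clinic. No variance figure supports it, and section 2.1 describes symptom ages that differ by sex, so age without gender is not an obvious choice. That stands; clinic is the main change.

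Fourth, the absence of bias concerns the omission of clinic only. The GLM's link and the handling of children who do not meet RTS by week 8 are unstated, and fitting clinic does not settle them.

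**Conclusion.** The concern holds. Clinic is the stratification factor and appears in no model, and the primary GLM names no baseline covariate. The consequence is a conservative test and slightly wide intervals, with no bias and no false-positive risk from the omission.

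In the simulations with normal outcomes at N = 126, fitting clinic gains about 0.5–0.8 power points at a 2% clinic share and 1.3–1.8 at 5%. At 10% and 20% it gains about 3 and 6 points, with at most 3.7 and 7.2 in any run. The low shares are the more plausible, so the likely gain is under 2 points. The size depends on the assumed share, on arms being balanced within clinics (block size is not stated) and on a mean-scale model. The change is worth making because the cost if clinic is irrelevant is about one patient, not because the trial is at risk without it.

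**What to change.** In 9.4.2, add clinic as a fixed effect in the primary time-to-RTS model. Set before unblinding a rule for pooling very small clinics, for example those with fewer than two patients in any arm; section 10.3 records two sites added later, so sizes may be unequal. State that group averages are standardised to the trial's clinic mix. With an identity link, clinic then does not change what the reported averages estimate.

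Add age as a prespecified covariate. Add visit-1 LEFS only if it is confirmed to be completed before randomisation: the schedule in 1.3 puts both at visit 1 without an order.

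If a stratified rank test is chosen instead, state that it can lose about 1 to 1.6 points when clinics are alike. The near-zero cost applies to a fixed effect, not to log-rank strata.

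Clinic may optionally go into the LEFS and Godin GEE models, which report means; that gain was not computed. It is not proposed for the FACES model, where it would change the odds ratio being estimated. Nor is it proposed for the adverse-event model, where it may be inestimable: with six clinics of 21 and an assumed 10% event rate, the chance that at least one clinic has no event is 50%.

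The cost is wording in 9.4.2 and no new data for clinic or age. The interim tests in 9.4.7 should use the same model and pooling rule. The degrees-of-freedom cost there is small: at N = 42 with an irrelevant clinic term, power is 32.3% instead of 32.6%.

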6.2.4 PREPARATION

DSP and 0.9% sodium chloride will be supplied by the CHKD Pharmacy Department in identical looking bottles, each containing 1.8 mL of solution and labeled in a blinded fashion as either Drug "A" or "B". Trained Therapists will be responsible for the preparation of the iontophoresis patches. Aseptic techniques will be utilized when preparing the patches. Upon randomizing a subject, the treating physical therapist will retrieve the appropriately labeled bottle ("A" or "B", based on the subject's randomization assignment) from the locked cabinet and check the expiration date. The treating physical therapist will apply 1.5 mL liquid (from the assigned bottle) to the negative side of the patch per the instructions listed in the I-Bresis Instruction for Use. The Therapist will then apply 1.5mL of 0.9% sodium chloride from the saline ampoules provided in the I-Bresis[™] carton to the positive side of the patch and will then obtain two patient identifiers (ex. Full name, DOB) from the patient prior to patch application per clinic policy.

The treatment site will be cleaned thoroughly with alcohol prep (ensuring the area being treated is free from other creams and topical medications, including topical steroids) as described in the instructions listed in the I-Bresis Instructions for Use.²³ The negative side of the patch will be applied over the tibial tubercle in patients with OSD and over the inferior patellar pole in patients with SLJ.

The I-Bresis controller will be turned on then connected to the patch. At that time, the start button will be pressed and the current will be initiated at 3mA for an initial 3minutes of treatment. Following this three minutes, the controller will be removed and turned off. The Patch will remain in place and an 80 mA-minute dose will be applied over two hours. The therapist will ensure that the patch fully conforms to the patient and that it will maintain full contact with the skin. To improve adhesion of the patch, the therapist may lightly wrap the patch with Pre-Wrap and secure the end with tape, ensuring the tape is not being applied over the patch so as not to bind it.

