8 STUDY ASSESSMENTS AND PROCEDURES

8.1 EFFICACY ASSESSMENTS

As Standard of Care:

- All patients who are referred to the participating PT clinics with a diagnosis of apophysitis of the knee and a prescription for PT with iontophoresis will receive a PT Initial Evaluation (IE).
 Per department policy, the PT IE must take place within 90 days of referral date as indicated on the script.
 - The IE includes: review of demographics, medical history, medication regime, strength and balance tests, pain assessment, review of home exercise program, icing instructions, activity restrictions, and bracing and NSAID instructions as recommended by their referring physician.
- After the IE, and as part of standard of care, all participants, regardless of group assignment, will receive a standardized PT treatment progression provided by qualified therapists.
 - As standard of care, PT progression visits may include up to 19 visits
- Clinic Check Visit Two (2) to three (3) business days after a participant is cleared for RTS, or has received treatment for eight (8) weeks, whichever is sooner, the participant will return to the

clinic for the Treating Therapist to confirm the participant remains pain free and able to meet the RTS criteria.

• Physical therapy progression visits to further fine tune mechanics, strength, and stretch may occur after this visit as part of their standard of care.

Study-related:

Study-related procedures will begin on the first PT Treatment Day, which may be the same day as the IE or at the next PT visit, but never before the Consent is signed. If subjects meet inclusion/exclusion criteria and the potential participant consents to participate at the Initial PT Evaluation Visit, the IE and Enrollment/Randomization Study Treatment Visit 1 visits may be combined.

The following procedures/evaluations will be obtained by the Treating Therapists:

- Lower Extremity Function Scale (LEFS) (see Appendix 12.1) a patient reported paper-based questionnaire that asks the patient to choose the level of difficulty of completing 20 different activities. Assessed at Study Treatment Visits 1, 5, 12/RTS Criteria Met Visit, and 30-day Follow Up. Note: the LEFS will be administered over the phone at the 30-day Follow-Up Visit.

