9.2 SAMPLE SIZE DETERMINATION

To assess the primary variable of interest, a power analysis indicated that a total sample of 126 participants would be required to detect medium effects (f = 0.28) with 80% power and $\alpha = 0.05$ using Generalized Linear Model (GLM).

The required sample size to test secondary hypotheses was calculated as 87 and 108 participants for patient reported outcomes and safety, respectively. Therefore, a total sample of 126 participants provides sufficient power for testing secondary hypotheses.

Given an estimated 15% non-compliance rate, the sample size will be increased by 15%, for a total sample size of 147 participants (49 per group).

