9.4 STATISTICAL ANALYSES

9.4.1 GENERAL APPROACH

Continuous variables will be expressed as mean, standard deviation, median, and range. Categorical variables will be presented as frequency and percentage. All statistical tests will be two-sided and p < 0.05 will be considered as statistically significant.

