9.4.6 SUB-GROUP ANALYSES

A Generalized Linear Model (GLM), including concomitant therapies, age, gender, and race will be conducted to analyze the possible effect of these covariates on length of time to RTS outcomes.

Generalized Estimation Equation model including concomitant therapies, age, gender, and race will be conducted to assess the effect of these covariates on LEFS, FACES, Godin Leisure-Time Exercise, and safety outcomes.

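### The primary GLM names no covariate; prespecifying center (the randomization stratum), pre-treatment LEFS and diagnosis could gain precision at almost no cost

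*Combined protocol and SAP*

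**What the plan says.** - **Primary model (9.4.2).** "A GLM will be conducted to test for significant difference in time to RTS (in days", comparing treatment groups. No covariate, family or link is named. Censoring is mentioned, but not how the GLM would handle it.
- **Covariate model (9.4.6).** "A Generalized Linear Model (GLM), including concomitant therapies, age, gender, and race will be conducted". This is a separate model under the sub-group heading. Center, diagnosis and baseline LEFS are not in it.
- **Randomization (6.3).** Stratified by center only. On allocation: "Equal number of participants per intervention will be considered to maximize study power". The synopsis gives six clinics.
- **Diagnosis.** Section 2.2 says that patients with either OSD or SLJ are randomized. Section 6.2.4 places the patch "over the tibial tubercle in patients with OSD and over the inferior patellar pole in patients with SLJ".
- **LEFS (8.1).** "Assessed at Study Treatment Visits 1, 5, 12/RTS Criteria Met Visit, and 30-day Follow Up".
- **Other uses of baseline data.** Section 9.4.5 compares baseline patient-reported outcomes across arms by ANOVA. The secondary GEE models in 9.4.3 include baseline records. The primary model does not.
- **Sample size (9.2).** "a total sample of 126 participants would be required to detect medium effects (f = 0.28) with 80% power", and after a non-compliance allowance "the sample size will be increased by 15%, for a total sample size of 147 participants (49 per group".

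**The concern.** The design balances the arms within clinics, but the primary analysis takes no account of clinic. When randomization is stratified, clinic differences are largely removed from the treatment comparison. An analysis without clinic still leaves them in the residual variance, so the standard error tends to be too large if clinics differ.

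Baseline function is a plausible predictor of the primary endpoint. LEFS (Appendix 12.1) rates squatting, running, sharp turns and hopping, and the RTS checklist (Appendix 12.3) requires pain-free squats, jumps, hops and a T-test. The plan uses baseline values for its secondary models and a balance check, but not for the primary endpoint.

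At stake are some power and some width of the confidence interval. Validity is not at stake.

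**Working it through.** **Inputs from the documents.** Three equal arms (6.3). N = 126, f = 0.28, power 80%, α = 0.05 (9.2). On sidedness, 9.4.1 says: "All statistical tests will be two-sided and p < 0.05 will be considered as statistically significant". Six clinics (synopsis). The calculation uses 126, the number before the 15% allowance.

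**Input not in the documents.** R², the share of within-arm variance in days to RTS that the covariates explain. It is assumed over a range that includes zero.

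**Step 1: reproduce the plan's figure.** Omnibus F test with df1 = 2, df2 = N − 3 and noncentrality λ = N·f².
- λ = 126 × 0.28² = 9.878, df2 = 123.
- Power = 80.02%, and 126 is the smallest N that reaches 80%. The stated figure is therefore the unadjusted three-group test and takes no credit for covariates.

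**Step 2: add covariates.** λ = N·f²/(1 − R²), df2 = N − 3 − c. LEFS and diagnosis use c = 2. Adding center uses 6 − 1 = 5 more, so c = 7. The confidence interval width relative to unadjusted is about √(1 − R²).

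| Assumed R² | λ | Power, c = 2 | Power, c = 7 | Relative CI width |
|---|---|---|---|---|
| 0 | 9.88 | 80.0% | 79.96% | 1.00 |
| 2% | 10.08 | 80.8% | 80.8% | 0.99 |
| 5% | 10.40 | 82.1% | 82.1% | 0.97 |
| 10% | 10.98 | 84.2% | 84.2% | 0.95 |
| 20% | 12.35 | 88.4% | 88.4% | 0.89 |

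**Step 3: the cost if the covariates explain nothing.** On degrees of freedom alone, power falls from 80.02% to 79.96%. Chance imbalance in LEFS and diagnosis, which are not stratified, adds a variance factor of about (126 − 3 − 1)/(126 − 3 − 2 − 1) = 122/120 = 1.017. Adjustment for those two therefore breaks even at an R² of about 1 − 120/122 = 1.6%.

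**Step 4: which covariate could matter (all values assumed).**
- *Diagnosis.* With SLJ share p and a difference of d standard deviations in time to RTS, R² = p(1 − p)d²/[1 + p(1 − p)d²]. For d = 0.5, p = 10% gives 0.0225/1.0225 = 2.2%, and p = 30% gives 0.0525/1.0525 = 5.0%.
- *LEFS.* A correlation of 0.3 to 0.5 with days to RTS gives R² = 0.3² to 0.5², that is 9% to 25%, or roughly 84% to 90% power.
- *Center.* If clinics explained 5% of the variance, leaving center out would inflate the standard error by about 1/√0.95 = 1.026, or 2.6%.

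**The case against.** The strongest reply is that the plan contains no error. Its sample size and its analysis agree, both unadjusted, and randomization protects the comparison. That stands. Several stronger readings do not.

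- *That the plan is known to be losing precision.* No section gives an R², a correlation, the OSD/SLJ mix or different recovery times. Section 2.1 describes SLJ as similar to OSD in mechanism, and a different patch site shows different anatomy, not different prognosis. The gain may be nil.
- *That chance imbalance biases the result.* It does not. The unadjusted interval and type I error already allow for it, and 9.4.5 would at least reveal an imbalance in LEFS.
- *That LEFS is known before treatment.* LEFS and the first patch both fall at Visit 1 and their order is not stated. FACES is taken at the end of each visit (8.1), so a pre-patch order cannot be assumed.
- *That diagnosis is already captured for everyone.* The Schedule of Activities lists no OSD/SLJ item, and patch site would show it only in Groups A and B.
- *That the power figures carry over to any model.* They assume an identity link and fully observed days. Study treatment stops at 12 treatments or 8 weeks, so some children may not be seen to reach RTS. In a non-linear or time-to-event model, adjustment can change the estimand as well as the precision.

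One could also say that 9.4.6 already adjusts. It omits all three variables, and it includes concomitant therapies, which 6.5 records at each treatment visit, so it is not a purely baseline-adjusted model.

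**Conclusion.** The point holds as a modest efficiency improvement. Center is the best-documented omission, because it is the stratification factor. Baseline LEFS is the covariate most likely to help, and diagnosis alone probably adds little.

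The gain at 126 participants runs from nothing (R² = 0) to about 8 power points (R² = 20%: 88.4% against 80.0%). It depends on an R² that the documents do not give and on a linear model with observed days. A reader might infer that the primary analysis is biased or the trial underpowered. Neither follows, since the unadjusted test is valid and 126 is the right number for it.

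**What to change.** 1. In 9.4.2, prespecify center and pre-treatment LEFS as covariates in the primary model, with diagnosis (OSD/SLJ) as a further covariate. Report the unadjusted result as a sensitivity analysis.
2. Keep the sample size unchanged.
3. State in 8.1 and the Schedule of Activities that the Visit 1 LEFS is completed before the first patch.
4. State that diagnosis is recorded at enrollment for all three groups.
5. If a non-linear or time-to-event model is adopted, name the adjusted estimand.

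**Cost.** SAP wording, two short protocol clarifications and, if diagnosis is not yet on a form, one data item. It needs no extra patients or visits. The statistical cost is a few degrees of freedom and a small allowance for chance imbalance. The covariates should be fixed before anyone sees outcome data by treatment group, because a later choice would be open to challenge.
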